Where and when will this procedure take place?

Participants will be recruited from the pool of people who have signed up for the mentoring group through WCNC. WCNC will advertise the mentoring group through their website and marketing materials as they do for other education classes they offer. Fathers who sign up for or express interest in the group program will be provided information about the associated research study by information posted on the WCNC website or by WCNC staff through verbal interaction, emails and/or flyers handed out at the clinic. Social media (e.g., Instagram/Facebook) postings made by department and clinic accounts will also be used to promote the study. Participation in the study is not required for those attending the mentoring group. Fathers attending the mentoring groups will be provided with links to listen to podcast episodes. Podcast listeners who have consented to participate in the study will be invited through the podcast website to complete brief satisfaction surveys about each podcast episode using their study ID.

Who will conduct this procedure?

Personnel

[name]

External User

Personnel
[name]

External User

Personnel
[name]

External User

Indicate the frequency and duration of visits/sessions as well as the subject's total time commitment for the study.

Describe how the data will be collected (i.e. in person or online).

Sign-ups for mentoring groups will occur online through the WCNC website.

Will any video, photography, or audio be recorded as part of this procedure?

No

Will data be collected anonymously?

No

Procedure Description
Screening and Consent

This procedure is:

Research Activity Involving Participants, Participants Data, or Biospecimens

This procedure is:

Where and when will this procedure take place?

All those who have decided to take part in the mentoring groups will be assigned an ID by WCNC staff. Potential participants will use this ID to complete an online screener survey. Those who are eligible will then be automatically provided consent information online through Qualtrics. Research staff will notify WCNC staff of the ID numbers of consented participants for management of survey distribution.

Who will conduct this procedure?

Personnel

[name]

Personnel

[name]

External User

Indicate the frequency and duration of visits/sessions as well as the subject's total time commitment for the study.

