Participants from the mentoring group or who are on a waiting list for the next mentoring group will be invited to complete electronic surveys at four time points over four months, with four weeks between each survey. A WCNC staff member ([name]) will send out a survey link to consented participants at each time point. Surveys will be available through [name]'s CSU Qualtrics account. Participants will enter their unique ID number in each survey so surveys can be linked over time. Surveys will assess demographics and outcomes of interest, including stress, mental health symptoms, parenting knowledge, confidence in parenting, the coparenting relationship, and satisfaction with their social networks. Participants will also be asked about whether or not they listened to podcasts.

Who will conduct this procedure?

Personnel

[name]

Personnel
[name]

External User

Indicate the frequency and duration of visits/sessions as well as the subject's total time commitment for the study.

15-30 minutes for each electronic outcome survey over 4 surveys. Total time: 1-2 hours.

Describe how the data will be collected (i.e. in person or online).

Online through Qualtrics

Will any video, photography, or audio be recorded as part of this procedure?

No

Will data be collected anonymously?

No

Procedure Description
Mentoring Program Satisfaction Surveys

This procedure is:

Research Activity Involving Participants, Participants Data, or Biospecimens

This procedure is:

Experimental

Where and when will this procedure take place?

Participants who have attended the mentoring program will be invited to complete an electronic satisfaction survey through [name]'s CSU Qualtrics account following completion of the group program. Surveys will ask about demographics, what participants liked or didn't like about the program, their perceptions of the group environment, and supportive group dynamics. Participants will also be given a brief (1-2 minute) electronic questionnaire at the beginning of each week of the program assessing their engagement in homework. Survey links will be sent by a member of the WCNC staff ([name]) to maintain separation of participant contact information from data. [name] will manage the data on the research side.

Who will conduct this procedure?

Personnel

[name]

Personnel

[name]

External User

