Identifiable information will only be accessible to WCNC staff. WCNC staff will provide ID numbers to each participant to use for completing their surveys. Research staff will only have access to participant ID numbers paired with survey data, not participant names or contact information. Survey responses will be aggregated for the purposes of reporting to community partners, stakeholders, publications, and grant reports. Given the small sample size, it is possible a person's data could be linked to their demographic information. To mitigate this risk, any data reported by demographic will be withheld if the demographic subgrouping contains a population of 3 or fewer people.

Clinical Trial

Will participants will be prospectively assigned to one or more interventions (including placebo or other control)?

Yes

Will the study evaluate the effects of the intervention on health-related outcomes (biomedical or behavioral)?

Yes

Does this study involve an FDA-regulated drug or device?

No

Will the study be conducted as a
Single-Site Clinical Trial

Will this study be posted on ClinicalTrials.gov?

Yes

ClinicalTrials.gov Registration# (or pending)

Pending

Additional information and support available through CSU Quality Assurance:

[contact]

Participant Population

Are you interacting or intervening with participants?

Yes

Provide an estimate of the anticipated participant total.

56

Are you analyzing existing data records or biospecimens?

No

Inclusion and Exclusion Criteria (e.g., Participants must have 20/20 vision, Participants must be 30-45 years of age, etc.) This should match your screening, consent, and recruitment materials.

Please list all inclusion criteria

Participants must be expecting a baby or have a baby less than one year of age and have signed up to participate in the DadSpace mentoring program at WCNC

Please list all exclusion criteria

Less than 18 years of age, non-English-speaking.

What is the rationale for studying the requested group(s) of participants?

These participants comprise the target population of people served by the clinic and the primary focus of the intervention.

Will you use a screening procedure, instruments, tools, questionnaires etc.?

Yes

Describe any planned screening procedures. Attach your screening document(s) (e.g., health history questionnaire), if applicable at the end of the form.

Participants will be screened for inclusion and exclusion criteria as listed above. Screening questions are attached.

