
Recruitment Process

Describe the procedures for identifying and recruiting potential research subjects or requesting pre-existing data or materials.

Participant Group Descriptor

DadSpace Mentoring Group members and wait-listed members

Please describe the recruitment process:

Marketing for the mentoring group will occur through traditional means, such as internet ads/postings, flyers/posters, face-to-face interactions, and email to clinicians and educators in related fields (e.g., pediatricians, OBGYNs, general practice, childbirth educators, doulas). Mentoring group information and sign-up will be available on the WCNC website alongside other class offerings WCNC provides. WCNC will assist in identifying potential subjects through their list of people who have signed up for the mentoring program. Recruitment information will also be available on the WCNC group website. Participants may also be recruited through emails or face-to-face interactions with WCNC staff.

Planned Subject Identification Methods

Direct advertising

Class participants

Referrals

Will a specific agency or institution provide access to prospective subjects?

Yes

Identify Agency

The Women's Clinic of Northern Colorado

Please select the recruitment personnel

[name]

Yes

Please list the external person(s) who will contact prospective students.

Prospective participants will be contacted by [name], [name], and/or [name].

Planned Recruitment Materials/Methods

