The default process for gaining consent is to use a signed form. Knowing that this does not always make sense, the IRB can approve alterations to what information is included, waive the requirement to get a signature or waive the requirement to obtain consent altogether when the request meets specific criteria.

Follow the prompts below to describe all consent processes and provide justification for any requested alterations or waivers.

Will informed consent be obtained from all research subjects (and/or their parents or legally authorized representatives)?

Yes

CSU Consent Personnel

[name]

No

Are you requesting a waiver of documentation of consent?

No

Consent

You do not have any procedures that include deception. If you are going to deceive or incompletely inform any subjects about any aspect of this study describe in the procedures section.

List each consent process

Who will obtain subjects consent?

Personnel

[name]

Which participant group is this consent process for?

All participants who agree to be involved in the mentoring program

How is consent being obtained?

WCNC staff will send a link to the electronic screener and study consent form to those who have signed up to participate in the mentoring group. [name] will confirm eligibility and receipt of consent and provide consent data to The Women's Clinic to house with participant identifiers.

Will non-English speaking participants be enrolled?

No

Program facilitation is being provided in English as with other programs WCNC offers, so it stands to reason that all participants will be able to understand and speak English.

Are any subjects unable to legally provide consent?

No

Conflict of Interests

For guidance on how to answer these questions and information please visit the [CSU Conflict of Interest page](#).

Does the research involve a drug, device, or biological invented by you, an immediate family member or other Research Personnel?

No

Is the research sponsored by an entity with which you, an immediate family member, or other Research Personnel have a paid consulting or advising relationship?

No

Will you, members of your immediate family, or other Research Personnel receive special compensation or increased compensation if the research generates a favorable outcome?

No

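### As written, fathers can know whether they are in a group or on the waiting list when they consent and answer survey 1; the plan should put both steps before placement and say so

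*Protocol*

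**What the plan says.** Sign-up for the class comes first. The inclusion criteria require that fathers "have signed up to participate in the DadSpace mentoring program at WCNC". The Recruitment procedure says "Participants will be recruited from the pool of people who have signed up for the mentoring group through WCNC", and the Recruitment Process section says "WCNC will assist in identifying potential subjects through their list of people who have signed up for the mentoring program". The Participant Group Descriptor in that section reads "DadSpace Mentoring Group members and wait-listed members".

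The Screening and Consent procedure then gives the sequence. It begins "All those who have decided to take part in the mentoring groups will be assigned an ID by WCNC staff"; the online screener follows, and eligible fathers go straight on to consent. The Consent section sends the link to "those who have signed up to participate in the mentoring group". After consent, the only step described is that research staff tell the clinic which IDs have consented, so that it can send out surveys.

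The Online Surveys procedure reads "Participants from the mentoring group or who are on a waiting list for the next mentoring group will be invited to complete electronic surveys". There are four such surveys, and survey 1 is not treated differently from the others. Joining the study is optional for fathers who attend the group (Recruitment). The Clinical Trial section answers yes to prospective assignment and gives neither method nor timing.

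The SAP compares 28 program fathers with 28 wait-list fathers in a 2 (time) by 2 (group) repeated measures ANOVA, with a stability coefficient of .50.

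**The concern.** A wait-list comparison is cleanest when fathers agree to take part and give their baseline answers before they learn which start they have. If they learn it first, two things can go wrong before the program begins.

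First, consent is a free choice. A father with a place and a father told to wait may weigh the surveys differently, so the two sets of consenters may differ in ways the pretest does not measure.

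Second, the outcomes (stress, mental health symptoms, parenting confidence and others) are self-reported online. Anticipation in one arm or disappointment in the other can shift the pretest answers themselves, and the pretest is one half of every gain score. The contrast at risk is the one that serves Study 1 Objective 2, which the protocol labels primary.

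**Working it through.** **Order of steps.** Setting the sections side by side:

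| Step | Where | Is placement mentioned? |
|---|---|---|
| Sign-up on the clinic website | Recruitment; inclusion criteria | No |
| ID from clinic staff | Screening and Consent | No |
| Screener, then consent | Screening and Consent; Consent | No |
| Consented IDs sent to the clinic | Screening and Consent | No; survey distribution only |
| Surveys 1 to 4 | Online Surveys | Yes; fathers are already in a group or on the waiting list |

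The descriptor in Recruitment Process applies the same two labels to the people recruited. No section puts placement after consent or after survey 1, and no section dates it at all. That fathers can know their arm at both steps is therefore the plain reading, not a stated fact.

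**Size.** The SAP has no figure on this point. Inputs from the SAP are r = .50 and 28 fathers per arm. Assumptions are that survey 1 is the SAP's pretest, SD = 1 at each time, no program effect, and a two-sided 5% test (the SAP states no alpha). Let b be the between-arm difference in pretest answers caused by knowing the arm, and k the share of it still present at posttest.

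- Gain contrast: the posttest difference is k × b and the pretest difference is b, so the bias is (1 − k) × b in size.
- Pretest-adjusted contrast: the posttest difference less r times the pretest difference is (k − r) × b.

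With k = 0 (a pretest-only shift) these are b and r × b in size. With k = 1 the gain bias is zero and the adjusted bias is (1 − r) × b = 0.5b. With k = .5 they are 0.5b and zero. Neither analysis is safe for every k, and k is unknown.

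For k = 0, the SD of a gain is √(2(1 − .50)) = 1, and the residual SD after adjustment is √(1 − .50²) = 0.866. The standard error is the SD times √(2/28) = 0.267. The noncentral t with 54 degrees of freedom, used for both, gives the chance of a significant difference in either direction:

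| b (SD) | Gain bias | Rejection rate | Adjusted bias | Rejection rate |
|---|---|---|---|---|
| 0.1 | 0.10 | 6.6% | 0.05 | 5.5% |
| 0.2 | 0.20 | 11.4% | 0.10 | 7.1% |
| 0.3 | 0.30 | 19.7% | 0.15 | 9.8% |

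The values of b are illustrative; nothing in the documents fixes them. Arm-dependent consent for reasons outside the pretest cannot be sized from the documents.

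**The case against.** The strongest reply is that no sentence puts placement before consent. The descriptor may be only a form label for who makes up the sample. IDs are issued without any split by arm, a single consent link serves everyone who signed up, and the Online Surveys wording may describe status across all four surveys rather than at survey 1. Consent at sign-up, before placement, is compatible with all of this. The listed attachments, such as the consent form and grant proposal, may also give the timing. This stands as far as it goes: it rules out stating as fact that arm is set before consent. It does not supply the missing order, and the procedure sections are where that order belongs.

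Two stronger readings are tempting. A reader might infer that the yes to prospective assignment contradicts the recruitment text. It does not, because it says nothing about when or how fathers are assigned.

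A reader might also infer a large, definite bias from stressed fathers on the wait-list consenting more readily. Suppose program fathers consent regardless of stress, half of wait-listed fathers consent, and their odds of consenting rise by a factor of 1.65 or 2.7 per SD of stress. The gain contrast then moves by about 0.12 or 0.20 SD. But the documents give no consent rates. At 70% to 90% wait-list consent the range falls to about 0.02 to 0.13 SD, and the direction reverses if less stressed fathers are the ones who consent. When consent depends only on the measured pretest, adjusting for the pretest removes the bias altogether. That figure therefore does not measure harm that only re-ordering can cure.

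**Conclusion.** The concern holds in a limited form. As written, nothing prevents fathers from knowing their arm when they consent and answer survey 1, and the plain reading is that they can. The harms that survive scrutiny are pretest answers shifted by that knowledge, and consent that differs by arm for reasons the pretest does not capture.

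The size and direction are unknown. A pretest-only shift biases the gain contrast by its full amount and the adjusted contrast by half of it at r = .50; any part of the shift that persists to posttest cancels from the gain. This rests on survey 1 being the pretest and on placement not coming later than the text suggests. The change is worth making because it is cheap and because arm-dependent refusal cannot be undone in analysis.

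**What to change.** In the Screening and Consent and Online Surveys procedures, state the order as sign-up, ID, screener, consent, survey 1 completed, and only then the clinic's confirmation of the coming group or the next one. Reword the Participant Group Descriptor to match, for example as fathers who have signed up and have not yet been given a start date. Report by arm how many fathers were approached, consented and completed survey 1; the IDs issued before screening make this count possible. If placement already follows survey 1 in practice, saying so and reporting the counts is enough.

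The cost is amendment wording for the IRB and a changed order of emails. The screener, consent and surveys are already online, and the clinic already sends the links. Start dates for a fee-charging class would be confirmed slightly later, and some fathers may already know their date from sign-up, so the protection will be incomplete. Re-ordering does not settle how fathers are placed in one group or the next; that is a separate question.

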***(All advertising must be submitted for review in its final printed/recorded form)**

Note: Attach copies of ALL recruitment materials in the attachment Section

Flyers/posters

Internet ads/postings

Email

Face to face interactions

Is there any possibility that potential participants may feel coerced to participate?

No

Is there any possibility that potential participants may feel undue influence to participate?

No

Participant Compensation/Costs

Will participants be compensated?

Yes

Form of Compensation

Gift Card/Certificate/Voucher

What is the approximate monetary value?

\$44 for the Intervention surveys, possibility to win \$25 for completing a podcast survey

Describe the remuneration plan.

Subjects will be paid for each survey they complete according to the following payment plan: \$8 outcome survey 1 \$10 outcome survey 2 \$10 outcome survey 3 \$10 outcome survey 4 \$6 mentoring group satisfaction survey

Subjects who complete podcast satisfaction surveys will be entered into a drawing each month to win one of two \$25 Amazon gift cards.

Will a 1099 be issued?

No

Will participants incur any costs to participate in this research?

Yes

Explain. This should be clearly outlined in the consent form.

Study participants will all have signed up to participate in the DadSpace mentoring program at the Women's Clinic of Northern Colorado. As with other classes WCNC offers, there is a fee to participate in the program. Class fees have not yet been set, but classes of similar length at The Women's Clinic run \$90.

Risks and Benefits

Minimal risk "means that the probability and magnitude of harm or discomfort anticipated in the research are not greater in and of themselves than those ordinarily encountered in daily life or during the performance of routine physical or psychological examinations or tests." [Department of Health and Human Services 45 CFR 46.102(j)]

Please indicate the researchers' evaluation of the overall risk level, and describe all known risks or discomforts associated with the study procedures, as prompted below. Note that any risks identified here should be consistent with risks you will disclose to participants in the consent process.

Minimal Risk

Are there risks associated with physical well-being?

No

Are there risks associated with psychological well-being?

Yes

Please describe.

While the level of risk is minimal, participants may become uncomfortable with some questions related to their experiences. They are allowed to decline to answer any question they feel uncomfortable with.

Are there risks associated with economic well-being, including employability?

No

Are there risks associated with social well-being, including reputational risks?

Yes

Please describe.

In a group setting, it is possible people in the group will know each other. If participants are not comfortable sharing their experiences during the group, they can choose not to say anything or remove themselves from the group.

Describe how the benefits of the research justify the likely risks to participants.

The group program and podcasts are research-informed to promote well-being and social support. Though psychological and social risks are possible, the risk is minimal compared to the potential benefits of participating in a program aimed at supporting fathers' successful adjustment before and after having a baby.

Describe direct research benefits to the participants, if any.

Risks in this study are minimal. The mentoring program and podcasts are designed to support positive outcomes in well-being and parenting for participants and their families. It is likely that any potential distress caused by surveys or social well-being will be outweighed by the benefits of the intervention and the supportive social environment.

Describe the indirect research benefits to society.

At the community level, the research may help refine the DadSpace mentoring program such that it becomes a sustainable and ongoing program to increase support resources for fathers. If the program is found to be feasible and efficacious, it may also help to inform future research for supportive fathering interventions. It is also possible the mentoring program could be adopted by other communities. Since podcasts are easily disseminated to a wide audience, podcasts may be useful to a variety of listeners, including perinatal fathers and those who help support them.

Data management plans, including plans for data sharing, are integral to project development. How you decide to collect, store, share and/or destroy data impacts your consent process, research procedures, data analysis, and publication.

Responses in this section constitute your plan. For guidance on how to answer these questions and plan for the data lifecycle, reference the resources and tools listed here.

[Data Management Services at CSU Libraries](#)

[General guidance and unfunded projects](#) (DMPTool)

[Funder-specific guidance and templates](#) (DMPTool)

If you choose to create a standalone data management plan (DMP) for your own purposes or at the direction of a funding agency, please attach that document to your protocol, also.

A [DMP fillable template](#) is available from CSU Libraries.

How will the data be stored and backed up during the research?

Initially, data will be managed and stored on Co-PI [name]'s password-protected Qualtrics account. Data will be downloaded from Qualtrics to a password-protected file folder in a secure HDFS research drive for statistical analyses (e.g., SPSS, Mplus). Access to this folder will only be granted to study personnel. Both Qualtrics and the PI's personal account are secure storage systems that are backed up regularly. A metadata repository will be developed for each study that describes the source of the data, a codebook for the demographic questions, syntax for computation of scale scores, and types of data files available (e.g., Excel, SPSS).

Who will be responsible for data and access management, and security?

Data Access Responsibility

[name]

Data Access Responsibility

[name]

Data Access Responsibility

[name]

Who will have access to study records or specimens?

Personnel

[name]

Personnel

[name]

Personnel

[name]

Will any external personnel have access to study records or specimens?

Yes

Please identify the external personnel with access to study records/data

WCNC staff ([name], [name], and [name]) will have access to participants' contact information and associated participant ID numbers. They will not have access to research data (survey data) associated with each participant ID.

How will you share the data?

Data outcomes will be reported in aggregate through reports to stakeholders and manuscripts. The availability of the data sets will be communicated to research peers and at conferences, and referenced in publications. The embargo period for the data sets restricting public access will be for two years from completion of the studies, and will be implemented in CSU's Digital Repository. Afterward, materials will be made available via persistent URLs configured for discovery by all major web crawlers.

Will identifiable data collected as part of the research be released in identifiable form? (e.g., pictures, recordings, responses to research questions, quotes)

No

Will the identifying information be destroyed at a specific date? For guidance, please reference any associated contract or grant (if applicable) and/or the [CSU Research Data Policy](#).

Yes

Destruction Date

August 1, 2031

What is the long-term preservation plan for the dataset?

After 2 years from completion of our study, we will archive the data in CSU's digital repository. We have no plans to submit data for open source access because as a CCTSI-funded project, the expectation is that we will use our findings to secure a larger extramural grant.

Do you intend to deposit your research data/specimens into a repository for future use?

Yes

If you already have a plan, please describe. Otherwise, you can enter N/A.

The data and related materials will be stored and preserved in CSU's open access digital institutional repository, a service jointly provided, operated, and managed by the CSU Libraries and the Department of Academic Computing and Networking Services. Because the total materials are <=1 TB in size, they will be stored, preserved, and made accessible at no cost to the project. The PIs will evaluate, distill, and select the data for preservation, and supply traditional and contextual metadata that will be reviewed and augmented as appropriate by librarians who are experts in digital repositories, including data and metadata organization and management. The CSU Digital Repository provides an exceptionally high-quality environment for data discovery, accessibility, transmissibility, and preservation. The CSU Libraries faculty and staff are experts in operating, managing, and sustaining digital data in formal repositories, possessing experience with multiple metadata schemes, harvesting of metadata and crawling of digital objects, digital rights management, and preservation.

Consent/Accord

Consent

The informed consent process involves presenting potential research participants with the key elements of a research study and what their participation will involve before they decide whether to participate. Please visit the [IRB website](#) for templates and guidelines on what information to include.

The default process for gaining consent is to use a signed form. Knowing that this does not always make sense, the IRB can approve alterations to what information is included, waive the requirement to get a signature or waive the requirement to obtain consent altogether when the request meets specific criteria.

Follow the prompts below to describe all consent processes and provide justification for any requested alterations or waivers.

Will informed consent be obtained from all research subjects (and/or their parents or legally authorized representatives)?

Yes

CSU Consent Personnel

[name]

No

Are you requesting a waiver of documentation of consent?

No

Consent

You do not have any procedures that include deception. If you are going to deceive or incompletely inform any subjects about any aspect of this study describe in the procedures section.

List each consent process

Who will obtain subjects consent?

Personnel

[name]

Which participant group is this consent process for?

All participants who agree to be involved in the mentoring program

How is consent being obtained?

WCNC staff will send a link to the electronic screener and study consent form to those who have signed up to participate in the mentoring group. [name] will confirm eligibility and receipt of consent and provide consent data to The Women's Clinic to house with participant identifiers.

Will non-English speaking participants be enrolled?

No

Program facilitation is being provided in English as with other programs WCNC offers, so it stands to reason that all participants will be able to understand and speak English.

Are any subjects unable to legally provide consent?

No

Conflict of Interests

For guidance on how to answer these questions and information please visit the [CSU Conflict of Interest page](#).

Does the research involve a drug, device, or biological invented by you, an immediate family member or other Research Personnel?

No

Is the research sponsored by an entity with which you, an immediate family member, or other Research Personnel have a paid consulting or advising relationship?

No

Will you, members of your immediate family, or other Research Personnel receive special compensation or increased compensation if the research generates a favorable outcome?

No

Will you, members of your immediate family, or other Research Personnel receive any money, gift or anything of monetary value above and beyond the actual costs of enrollment, conduct of the research, and reporting on the results, including, but not limited to, finders fees, referral fees, recruitment bonuses, and an enrollment bonus for reaching an accrual goal or similar types of payments?

No

Do you, members of your immediate family or other Research Personnel have any other interests or relationships (including volunteer services) that might constitute a conflict of interest or an appearance of conflict of interest in connection with the research project?

No

Will the payment you receive for services provided during the conduct of the research (e.g., investigator and Research Personnel time and tests) be inconsistent with fair market value for those services?

No

Significant Financial Interest: Please check Yes or No for each item below.

Will you, your immediate family members or other Research Personnel receive salaries, royalties and/or other payments for services (e.g., consulting fees, honoraria, research design, management position, independent contractor, service on advisory or review committees, board membership seminars, lectures or teaching engagements when totaled together exceeded \$5,000 during the previous 12 months or are expected to exceed \$5,000 over the next 12 months)? This excludes reasonable costs of conducting the research, as specified in the research agreement.

No

Do you, your immediate family members, or other Research Personnel hold any ownership interests including stocks, bonds, or stock options that exceed \$5,000 and/or that constitute more than a five percent (5%) ownership interest in the sponsoring organization? This does not include any interests held solely by reason of investment in a business by a mutual, pension or other institutional investment fund over which the investigator and/or his or her immediate family do not exercise day-to-day control of investment decisions.

No

Minimizing Risks and Disclosure to Subjects

Have you disclosed any actual, potential or perceived conflicts of interest in the consent form? Research Personnel are required to disclose all such conflicts to all research participants in the research consent form.

Yes

By submitting this form, you are attesting that you have read [Colorado State University's policy on Conflict of Interest](#) and agree to abide by its terms. You will update this disclosure form when new or changes in conflict of interest arise, and that you will comply with any conflict management plan required by the Institutional Review Board (IRB) to manage, reduce, or eliminate any actual or potential conflict of interest for the duration of the research.

Attachments

Attach all relevant documentation to your research in this section. Please label each item appropriately, so your IRB reviewers understand the purpose and population each document aims to address. Please delete the existing attachment and upload the Tracked Changes version and Clean revised document for review to update or revise any existing attachments.

Any documentation that a participant will see must be reviewed and approved by the IRB, including consent, recruitment, communications, tools, instruments, etc. Additional documents required for review include funding proposals, contracts, letters of agreement, methodology, related approvals, etc. For more information and guidance on what documentation to attach, please visit the IRB website.

Answers within your application indicate that the following documentation is required:

